14.7 Quality Control and Quality Assurance of Study Data

14.7.1 Data Processing and Data Quality Assurance

All site-generated study data are entered into an eCRF via an EDC system. Site personnel enters data from assessments performed as part of the standard of care for their patients who are taking Revcovi. These assessments include height and weight measurements, vital signs, and safety and specialty laboratory test results. The data are entered into specific time periods (e.g., Baseline, month 3, month 6, etc) that are defined relative to the Revcovi start date. Patients are also assessed throughout the duration of the registry for any concomitant medications, hospitalizations, procedures, and AEs, and that information is also entered into the EDC system. There are automatic system queries based on programmed edit checks, and there are manual queries that result from review of the data by the data manager, CRA, or other project team members. System queries include future dates, out of window dates, and out of range vital signs. Manual queries include cross-form checks, duplicate dates, and discrepant information.

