5. GENERAL ANALYSIS CONSIDERATIONS

All analysis will be descriptive and no statistical hypothesis will be tested. Descriptive statistics for continuous variables will include number of observations (n), mean, standard deviation (SD), median, minimum (min), and maximum (max); for categorial variables counts and percentages for each category. Ninety-five percent confidence intervals (CIs) will be calculated for the main outcome variables without adjustment for multiplicity to generalize the results to the general population. If not otherwise noted, confidence intervals for continuous variables will be based on normal distribution, for categorial variables on Clopper-Pearson (Clopper and Pearson 1934). Confidence intervals for Poisson distributions will be calculated by the method of Ulm (Ulm 1990).

Time to event analyses will be performed by the Kaplan-Meier method (Kaplan and Meier 1958). Confidence intervals for the median survival time will be calculated based on the method of Brookmeyer and Crowley (Brookmeyer and Crowley 1982) after log-log transformation.

All analyses will be performed by subject status (Adagen-Naïve subject, Adagen-Transitioning subject, or STP-2279-002 participant) and overall. Subject status is as collected on the Adagen/Revcovi Treatment page in the eCRF. There is a different recommended visit schema for the Adagen naïve subjects and the Adagen transitioning subjects (Table 1 and Table 2). However, a data review revealed that the timing of the assessments is not following the suggested visit schema. Therefore, the slotting schema within each subject status will be uniform for all assessments. All assessments will be slotted to the closest visit suggested for the Adagen transitioning or Adagen naïve subjects, respectively, regardless of whether or not the specific assessment is recommended for this visit, Participants of the STP 2279-002 study will be analyzed per the Suggested Schedule of Assessments for Adagen-Transitioning Subjects. Therefore, the visit windows will be specific for each type of subjects (see Section 13.3). All visits will be included in the overall column, regardless of whether or not the specific visit is analyzed for all type of subjects.

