13.3 Baseline and Assignment to Suggested Study Visits

For Adagen-naïve patients and Adagen-transitioning patients, baseline will be defined as the last measurement for a variable with a non-missing value prior or on the treatment start date with Revcovi in this study (CLI-06814AA1-01). For STP 2279-002 subjects, the baseline will be defined as the last measurement for a variable with a non-missing value prior or on the treatment start date with Revcovi in STP 2279-002. At Study Day 1, it is assumed that all assessments are performed prior to the application of the first dose of Revcovi. However, adverse events with the same onset date as the start date of Revcovi will be assumed to be post-treatment and counted as treatment-emergent AEs.

Assessments will be 'slotted' to the treatment visits as described below. Reference date for all visits will be the start date of Revcovi (Study Day 1). Study Day 1 for the subjects transitioning from the STP-2279-002 study will be the reported start date of Revcovi in the STP-2279-002 study. Depending on the subject status (Adagen-Naïve subject or Adagen transitioning subject), the suggested visit schedule is different for the first 9 treatment months. For the Adagen-Naïve subjects, there are more suggested visits compared to the Adagen transitioning subjects. Participants of the STP 2279-002 study will be analyzed according to the Schedule of Assessments for Adagen-Transitioning Subjects. The visit windows will be defined for all assessments as follows:

Suggested Visit	Targeted Study Day	Visit window (Study Day)					
Enrollment/Baseline	Last available data	$-\infty$ to 1					
	prior or at Study Day 1						
TW 4	30	2-45					
TW 8	60	46-75					

Adagen-Transitioning subjects

Chiesi Farmaceutici S.p.A. Statistical Analysis Plan CLI-06814AA1-01 Version 4.0 06June2023

TM 6 TM 9 TM 12	182 273	137-227 228-319
		228-310
TM 12		
	365	320-410
TM 15	456	411-501
TM 18	547	502-592
TM 21	638	593-684
TM 24	730	685-776
TM 27	822	777-867
TM 30	913	868-958
TM 33	1004	959-1049
TM 36	1095	1050-1141
TM 39	1187	1142-1232
TM 42	1278	1233-1324
TM 45	1370	1325-1415
TM 48	1461	1416-1506
TM 51	1552	1507-1597
TM 54	1643	1598-1689
TM 57	1735	1690-1780
TM 60	1826	1781-1871
TM 63	1917	1872-1962
TM 66	2008	1963-2055
TM 69	2100	2056-2145
TM 72	2191	2146-2236
TM 75	2282	2237-2328
TM 78	2374	2329-2419
TM 81	2465	2420-2510
TM 84	2556	2511-2601
TM 87	2647	2602-2693
TM 90	2739	2694-2784
TM 93	2830	2785-2875
TM 96	2921	2876-2966
TM 99	3012	2967-3057

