14. PROGRAMMING SPECIFICATIONS

- The following algorithm should be used to estimate adverse event start dates for which only partial information is known. To conservatively assign start dates as early as possible, the first day on study drug is the reported start date of Revcovi in the CLI-06814AA1-01 study.
 - Missing day and month
 - If the year is the same as the year of first day on drug, then the day and month of the start date of drug will be assigned to the missing fields.
 - If the year is prior to the year of first day on drug, then December 31 will be assigned to the missing fields.
 - If the year is after the year of first day on drug, then January 01 will be assigned to the missing fields.
 - Missing month only
 - Treat day as missing and replace both month and day according to the above procedure.
 - o Missing day only
 - If the month and year are the same as the year and month of first day on drug, then the start date of drug will be assigned to the missing day.
 - If the month and year are before the year and month of first day on drug, then the last day of the month will be assigned to the missing day.
 - If the month and year are after the year and month of first day on drug, then the first day of the month will be assigned to the missing day.

If the resultant imputed start date is after the AE stop date (and the AE stop date is complete), the imputed start date will be reset to the AE stop date.

- Adverse events with partially missing stop dates and the outcome is "Resolved" or "Resolved with sequelae" will have stop dates imputed as follows:
 - *year is missing* date left missing.
 - o month is missing impute 'December'.
 - o *day is missing* impute 'last date of that month'.

- It is assumed that for the start and stop date of Revcovi, at least month and year are known. If day is missing, it will be imputed by the first of the month, if necessary.
- Partially missing start dates for Adagen pre-treatment (Adagen transitioning patients) will be imputed as follows:
 - Day is missing impute 01 of the month
 - Day and month is missing: impute 01July.
- It is assumed that at least month and year is known for the QoL questionnaires, physical examinations, vital signs, and other laboratory data. If the day is missing, day will be imputed by the 15th of the month. If month and/or year is missing, the records will be excluded from all analyses.
- Partially missing dates for the diagnosis of ADA-SCID will be imputed as follows:

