 - Year is missing impute with date of birth
 - Month is missing and year is available impute by 01 January. If the imputed date is prior to the date of birth, impute date of birth.
 - Day is missing impute first day of month. If this imputed date is prior to the date of birth, impute date of birth.
- Complete dates for concomitant medications with missing or partially missing start dates will be imputed, if necessary, using the same algorithm described for adverse event onset dates. If the stop date is missing or partially missing and the "ongoing" variable is indicated as 'no', the imputation rule is applied in the following order:
 - *year is missing* the medication will be considered to have been received at all periods after that period determined by the start date. Date is left missing.
 - o month is missing impute 'December'.
 - o *day is missing* impute 'last date of that month'.
- The following algorithm should be used, when necessary, to calculate a start date that is partially missing for medical history:
 - missing day and month January 01 will be assigned to the missing fields.
 - *missing month only* treat day as missing and replace both month and day according to the above procedure.
 - *missing day only* assign first of the month to the missing day.
- Partially missing stop dates will be imputed as:
 - *year is missing*, no imputation. Date left missing.

- *month is missing and year is prior to year of first dose of study medication*impute 'December'.
- month is missing and year the same as the year of the first dose of study medication impute same month as in start date.
- \circ day is missing: impute 'last date of that month'. If this results in a date \geq the date of the first dose of study medication, impute day as the day prior to the first dose of study medication.
- Partial missing death dates will be imputed in the same way as adverse event start dates.
- Date imputations will be applied to the process of assigning study day and should be retained in the analysis datasets, but the data listings should display the original, partially missing dates.
- Adverse event summary tables will only include treatment-emergent AEs. However, listings will include all AEs (i.e., treatment-emergent and non treatment-emergent AEs) with the non treatment-emergent AEs flagged.

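### SAP 14 sets a missing assessment day to the 15th without checking it against the Revcovi start, so records from the month of first dose can fall on the wrong side of baseline

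*SAP*

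**What the plan says.** SAP 14 gives one rule for several kinds of assessment: "It is assumed that at least month and year is known for the QoL questionnaires, physical examinations, vital signs, and other laboratory data". It continues: "If the day is missing, day will be imputed by the 15th of the month". The rule has no condition on the Revcovi start date.

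The imputed date is then used in the analysis. SAP 14 says: "Date imputations will be applied to the process of assigning study day and should be retained in the analysis datasets". For Adagen-naïve and Adagen-transitioning subjects, SAP 13.3 defines baseline as the "last measurement for a variable with a non-missing value prior or on the treatment start date with Revcovi in this study", and adds: "At Study Day 1, it is assumed that all assessments are performed prior to the application of the first dose of Revcovi". Visit assignment also goes by date. SAP 5 states: "All assessments will be slotted to the closest visit suggested for the Adagen transitioning or Adagen naïve subjects".

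The protocol describes a second source of timing, in section 14.7.1: "The data are entered into specific time periods (e.g., Baseline, month 3, month 6, etc) that are defined relative to the Revcovi start date". The SAP does not use that recorded period to assign baseline or visits.

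Other date rules in SAP 14 do have bounds. Adverse event start dates depend on the month and year of first drug intake, and concomitant medication starts and death dates follow the same algorithm. Medical history stop dates are held before first dose. Diagnosis dates cannot precede birth.

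**The concern.** In the month of first dose, the 15th can lie before or after the start. Which side a day-missing record falls on then depends only on the start day, not on when the sample was taken.

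Baseline enters the change from baseline for dAXP and ADA activity (SAP 7.2.1), immune status (7.2.2), growth z-scores (7.2.3), laboratory tests (8.3) and vital signs (8.4). An on-treatment value used as baseline shrinks or distorts that subject's change. A pre-dose value moved past Day 1 may leave the subject with no baseline, or with an older one. Results are split by three subject statuses and no sample size is set (SAP 3.2 and 5), so a single record could move a small-group mean.

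Partial dates are plausible. Protocol 7.1 and 11.1 allow data from before enrollment to be collected retrospectively, and SAP 14 itself provides for missing days.

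**Working it through.** The plan gives no figure on this point, so there is nothing to reproduce. I applied its own rules.

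**Inputs**
- Study day = date − start date, plus 1 if the difference is ≥ 0 (SAP 13.2).
- A missing sample day becomes 15 (SAP 14).
- A value is baseline-eligible if its study day is ≤ 1 (SAP 13.3).
- Assumption: start day and sample day are independent and uniform over the month. The documents give no distribution.

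**Two examples, with sample and start in the same month**

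| Start day | True sample day | True study day | Imputed study day | Result |
|---|---|---|---|---|
| 20 | 28 | 28 − 20 + 1 = 9 | 15 − 20 = −5 | on-treatment sample becomes baseline-eligible |
| 10 | 8 | 8 − 10 = −2 | 15 − 10 + 1 = 6 | pre-dose sample becomes on-treatment |

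**General pattern.** For a start on days 1 to 14, the imputed study day runs from 15 down to 2, so every pre-dose sample is moved past first dose. For a start on day 15 or later it is at most 1, so every on-treatment sample becomes baseline-eligible.

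**Enumeration, 30-day month (30 × 30 = 900 pairs)**
- True pre-dose pairs (sample day ≤ start day): 1 + 2 + … + 30 = 465. True on-treatment pairs: 900 − 465 = 435.
- On-treatment to baseline-eligible (start 15 to 30): 15 + 14 + … + 0 = 120, which is 120/435 = 27.6% of on-treatment samples.
- Pre-dose to on-treatment (start 1 to 14): 1 + 2 + … + 14 = 105, which is 105/465 = 22.6% of pre-dose samples.
- Total: 225/900 = 25.0%.

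Month length hardly matters: (91 + 105)/784 = 25.0% for 28 days and (136 + 105)/961 = 25.1% for 31 days.

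**What happens to a pre-dose value that is moved.** SAP 13.3 keeps the value closest to the target day in each window. The Week 2 target for naïve subjects is Day 15. The imputed day is 16 − start day, so it lies within 3 days of the target only for starts on days 1 to 4. That is 1 + 2 + 3 + 4 = 10 of the 105 pairs (9.5%). The other 95 lose to any real sample taken on Days 12 to 18. For transitioning subjects the first target is Day 30, and the imputed value can be no later than Day 15, so a real Week 4 sample would normally replace it. The main harm in this direction is therefore the lost baseline, not a contaminated visit.

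**The case against.** Several objections have force.

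- **Frequency is unknown.** The error needs a missing day and a sample in the start month. Nothing in the documents shows how often that happens. Protocol 14.7.1 also provides queries for out-of-window dates and discrepant information, which may reduce the number. These queries act on entered data and do not check the date imputed later.
- **Displacement is conditional.** A mis-dated on-treatment value replaces the true baseline only if no other value is dated from the 15th up to the start. This stands.
- **Consequences are limited.** All analyses are descriptive, and the listings show the original partial dates, so affected records can be traced. The summary tables would not reveal them.
- **QoL is largely outside the point.** SAP 9 says QoL data will be listed and not summarized, although its next sentence still mentions summarized changes.
- **STP-2279-002 participants** have Study Day 1 in the earlier study (SAP 13.2 and 13.3), so their registry samples are unlikely to be affected at baseline.

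Two stronger readings are tempting. A reader might infer that the missing start-date check also explains day-missing records falling into the wrong early visit windows of naïve subjects. It does not. That comes from placing a month-only date into windows of about 15 days, and a check at first dose would barely change it. A reader might also infer that the Enrollment record can simply be taken as pre-dose, since SAP 13.3 labels the first slot Enrollment/Baseline. Protocol 7.1 rules this out: enrollment is the consent date, and some subjects are already on Revcovi by then.

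**Conclusion.** The point holds for a narrow set of records: physical examination (through height and weight), vital-sign and laboratory records with a missing day, dated in the month of first dose. For these the written rule can reverse the order of sample and first dose, in both directions, and no other SAP rule corrects it.

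The 25% is the chance of misclassification for one such record under uniform, independent days. It is not a share of all records or of all baselines, and it could be higher or lower under other day patterns. The documents give no count from which to derive an overall effect. The matter deserves correction because baseline feeds many tables, the SAP already bounds comparable dates, and the remedy is cheap.

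**What to change.** Add to SAP 14, for assessments with a missing day whose month equals the month of first Revcovi dose (the Study Day 1 reference for that subject):

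1. Class the record as pre-dose or post-dose from its eCRF period, but only where that period is defined relative to Revcovi start. A Baseline record is placed no later than Study Day 1, and a post-baseline record no earlier than Study Day 2.
2. Do not treat Enrollment as pre-dose for subjects who started Revcovi before consent or in STP-2279-002.
3. If the period does not settle the order, list the value but use it neither as baseline nor in by-visit summaries.

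Where the recorded period is available and correct, misclassification among the 900 pairs falls from 225 to 0. Date-based slotting otherwise stays as it is. The cost is a few SAP sentences and a small programming change, and a few ambiguous records will drop out of the tables. A count of day-missing records in the start month, reported with the results, would show whether the issue had any practical effect.

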5.1 Disease Background

Adenosine deaminase (ADA)-deficient combined immunodeficiency disease is a rare, inherited, and often fatal disease. It is characterized by severe and recurrent opportunistic infections, failure to thrive, profound lymphopenia with absent or severely impaired cellular and humoral immune function, and metabolic abnormalities (Booth and Gaspar 2009, Gaspar et al., 2009). These patients are lymphopenic at birth and predisposed to recurrent illnesses caused by pathogens and opportunistic organisms that often begin within a few weeks. The average age at diagnosis for patients with ADA-SCID is within first few months of life (Arredondo-Vega et al., 1998). The incidence of ADA deficiency is estimated to be between 1:200,000 and 1:1,000,000 live births (Gaspar et al., 2009).

ADA deficiency can be categorized into four phenotypes (Booth and Gaspar 2009):

- **Early onset**: The largest number of patients with ADA deficiency (about 85% to 90%) present with early onset ADA-SCID, which is the most severe form of the immunodeficiency. Patients are usually diagnosed within first few months of life and almost always by the age of 1 year.
- **Delayed onset ADA deficiency** has been identified in 10% to 15% of patients with ADA deficiency. The disease presents itself after the first year of life and is most likely related to the specific ADA mutation that in such cases results in some residual ADA activity and less profound lymphopenia and immune function.
- Late (or adult) onset ADA deficiency has been identified in some individuals but is less common than early or delayed-onset forms.
- **Partial ADA deficiency** can be an incidental finding in a healthy individual who has normal immune function and abnormal ADA expression in erythrocytes. Partial ADA deficiency is extremely rare.

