6.4 Disease Background and History

Disease background will also be summarized at screening by subject status and overall. Missing categories will be presented if applicable. Disease background includes age at first diagnosis of ADA-SCID (years), time from first diagnosis of ADA-SCID to start of Revcovi treatment in the STP 2279-002 study, if applicable, (months), and availability of ADA-SCID mutations. All parameters will also be listed. Missing categories will be presented if applicable.

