TM 102	3103	3058-3148
TM 105	3194	3149-3240
TM 108	3286	3241 or later
1-month post-	30	1-60
transplantation*		

6-month post-	182	61 onwards
transplanation*		

*Reference date for the 1- and 6-month post-transplantation visit is the date of the last dose of REVCOVI

Suggested Visit	Targeted Study day	Visit window
Enrollment/Baseline	Last available data	-∞ - 1
	prior or at Study Day 1	
TW 2	15	1-22
TW 4	30	23-37
TW 6	45	38-52
TW 8	60	53-67
TW 10	75	68-83
TW 12	91	84-106
TM 4	121	107-136
TM 5	151	137-166
TM 6	182	167-197
TM 7	212	198-227
TM 8	242	228-257
TM 9	273	258-319
TM 12	365	320-410
TM 15	456	411-501
TM 18	547	502-592
TM 21	638	593-684
TM 24	730	685-776
TM 27	822	777-867
TM 30	913	868-958
TM 33	1004	959-1049
TM 36	1095	1050-1141
TM 39	1187	1142-1232
TM 42	1278	1233-1324
TM 45	1370	1325-1415
TM 48	1461	1416-1506
TM 51	1552	1507-1597
TM 54	1643	1598-1689
TM 57	1735	1690-1780
TM 60	1826	1781-1871
TM 63	1917	1872-1962
TM 66	2008	1963-2055

Adagen-Naïve Subjects

6-month post- transplanation*	182	61onwards
1-month post- transplantation*	30	1-60
TM 108	3286	3241 or later
TM 105	3194	3149-3240
TM 102	3103	3058-3148
TM 99	3012	2967-3057
TM 96	2921	2876-2966
TM 93	2830	2785-2875
TM 90	2739	2694 or later
TM 87	2647	2602-2693
TM 84	2556	2511-2601
TM 81	2465	2420-2510
TM 78	2374	2329-2419
TM 75	2282	2237-2328
TM 72	2191	2146-2236
TM 69	2100	2056-2145

*Reference date for the 1- and 6-month post-transplantation visit is the date of the last dose of REVCOVI

For by-visit summaries, if there are multiple assessments in the specified time windows, the value most closely to the targeted time point will be used for the analysis. If 2 timepoints have the same distance from the targeted time point, the value after the targeted timepoint will be used for the analysis.

Missing data will not be imputed.

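### An ADA-SCID diagnosis date with a missing year is imputed as the date of birth, so that subject's age at diagnosis is reported as 0 whatever the true age

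*SAP*

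**What the plan says.** SAP 14 introduces the rules with "Partially missing dates for the diagnosis of ADA-SCID will be imputed as follows" and then gives three cases.

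- Year unknown: "Year is missing impute with date of birth".
- Year known, month unknown: "Month is missing and year is available impute by 01 January", followed by "If the imputed date is prior to the date of birth, impute date of birth".
- Only the day unknown: "Day is missing impute first day of month. If this imputed date is prior to the date of birth, impute date of birth".

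The date feeds two summaries in SAP 6.4. Age at first diagnosis, in years, is produced for everyone. Time from diagnosis to the start of Revcovi in STP-2279-002, in months, is produced only where applicable. Both are shown by subject status and overall, and SAP 6.4 provides for missing categories to be presented. Under SAP 14, imputed dates stay in the analysis datasets while listings show the original partial dates. The SAP asks for no count or flag of imputed diagnosis dates in the tables.

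**The concern.** A date of birth is not an estimate of an unknown diagnosis year. It is the earliest value possible, and it turns missing information into a definite statement that the subject was diagnosed at birth. In this disease that value carries meaning. The registry enrols infants found by newborn screening as well as patients on chronic ERT. Protocol 5.1 describes a delayed-onset form in 10% to 15% of patients, of which it says "The disease presents itself after the first year of life", and a rarer adult-onset form. A late-diagnosed subject with no recorded year would be indistinguishable in the table from a screened newborn.

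At stake is the accuracy of a background description by subject status. No efficacy or safety result depends on it.

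**Working it through.** The documents state no figure for this point, so there is nothing to reproduce. The check applies the rule.

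**Direction and size, year missing.** Imputed date = date of birth. Imputed age at diagnosis = 0. Error = 0 − *a* = −*a*, where *a* is the true age at diagnosis. For an STP-2279-002 subject, time from diagnosis to Revcovi rises by 12*a* months.

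The documents give no distribution for *a*, so three uniform ranges are assumed. The mean understatement is the midpoint of each range:

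- 0 to 90 days: (0 + 90)/2 = 45 days.
- 0 to 365 days: (0 + 365)/2 = 182.5 days.
- 366 to 1,826 days (1 to 5 years): (366 + 1,826)/2 = 1,096 days, about 3.0 years.

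The imputed age is 0 in 100% of cases in all three.

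**Effect on a column mean.** One affected subject among *n* shifts the mean by −*a*/*n*. The registry's *n* is not stated, so 30 and 6 are assumptions. The value 6 is the denominator used for adverse reactions in the Adagen lead-in study described just before Protocol 5.3.2.2. That study is apparently STP-2279-002, and all 6 would have to enrol for the column to be this size.

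| True age *a* | n = 30 | n = 6 |
|---|---|---|
| 0.25 years | 0.25/30 = 0.008 years | 0.25/6 = 0.04 years |
| 3 years | 3/30 = 0.10 years | 3/6 = 0.5 years |
| 10 years | 10/30 = 0.33 years | 10/6 = 1.7 years |

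The minimum, which SAP 5 includes among the descriptive statistics, becomes 0 with a single affected subject.

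**Month and day rules, for comparison.** Imputed date = the later of the start of the known year or month and the date of birth. With 100,000 simulated diagnosis dates per range and birthdays spread evenly over the calendar (assumption):

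| True age range | Month missing: mean understatement | Imputed age exactly 0 | Day missing: mean understatement |
|---|---|---|---|
| 0 to 90 days | 41 days | 88% | 13 days |
| 0 to 365 days | 122 days | 50% | 14 days |
| 1 to 5 years | 182 days | 0% | 15 days |

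These errors are also one-sided, but they are bounded: at most 365 days with the month missing and 30 days with the day missing. The missing-year error has no bound other than the subject's own age at diagnosis.

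**How the SAP treats a missing year elsewhere.** Stop dates for adverse events, concomitant medications and medical history are left missing. Laboratory, vital-sign and QoL records without a month or year are excluded from analysis. The diagnosis date is treated differently, and no reason is given.

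**The case against.** The strongest reply is that little turns on this. All analyses are descriptive and no hypothesis is tested. Protocol 5.1 puts 85% to 90% of patients in the early-onset group, diagnosed within months of birth, so birth is close to the truth for most. No count of missing years is given, and it could be zero. The listings show the original partial dates. All of this stands and limits the weight of the point, but it does not make age 0 a correct entry for a subject whose year is unknown.

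Several stronger readings are tempting, and the documents do not support them.

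- A reader might infer that a wholly unknown date is certainly set to birth. The rules are introduced as covering partially missing dates, so the handling of a wholly missing date is unclear.
- A reader might infer that a missing month also produces age 0. It does so only when the known diagnosis year is the birth year.
- A reader might see a contradiction with "Missing data will not be imputed" in SAP 13.3. That sentence closes the visit-window rules, and Protocol 13.2.3 allows the SAP to specify exceptions. SAP 14 is such a specification.
- A reader might extend the effect on time to Revcovi to all groups. SAP 6.4 defines that variable only for STP-2279-002 subjects.
- A reader might suppose that older patients are the ones lacking dates, or that age at diagnosis defines analysis groups. No passage says the first. On the second, SAP 5 takes subject status from the eCRF treatment page.
- A reader might want midpoints for month and day as well. That is a trade-off. With the month missing, true age uniform on 0 to 90 days and no bound from the first ERT dose, a midpoint between the earliest possible date and 31 December gives a bias of +2.3 months and a mean absolute error of 2.4 months. The existing rule gives −1.4 and 1.4. At 1 to 5 years the midpoint is better (mean absolute error 3.0 against 6.0 months).

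**Conclusion.** The point holds for the missing-year rule. It assigns age 0 at diagnosis to any subject it is applied to and understates age by the full true value. For STP-2279-002 subjects it overstates time from diagnosis to Revcovi by the same amount. This follows directly from the rule, assuming only that diagnosis is not before birth. The error is a matter of months or less for subjects diagnosed in the first months of life, and can be years for delayed or adult onset. How far it moves a reported mean depends on column size and on the number affected, neither of which the documents give. The consequence is a misleading background table, not a biased treatment result. The month and day rules are defensible and need only disclosure.

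**What to change.** In SAP 14, replace the missing-year rule: if the year of diagnosis is unknown, including when the whole date is missing, the date stays missing. Exclude the subject from the age-at-diagnosis and time-from-diagnosis statistics, and show the subject under a missing category in SAP 6.4. Leave the month and day rules as they are, and footnote in the table how many diagnosis dates had month or day imputed.

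The cost is a few lines of SAP text, one changed derivation and one footnote. The downside is that slightly fewer subjects contribute to the two summaries.
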